Study drug/ treatment	Any single drug or combination of drugs administered to the patient as part of the required study procedures; includes investigational drug (s), active drug run-ins or background therapy
Study/investigational treatment discontinuation	Point/time when patient permanently stops taking study/investigational treatment for any reason; may or may not also be the point/time of premature patient withdrawal
Variable	Information used in the data analysis; derived directly or indirectly from data collected using specified assessments at specified time points

Amendment 5

Changes to the protocol are related to the following sections:

- Section 4.1. inclusion criteria

The current version of inclusion criteria stipulates that *"patients who have completed the international CACZ885G2306 study and who successfully withdrew canakinumab treatment per protocol but with a disease relapse within one year from the End of study visit will be allowed to participate in CACZ885GFR01 study"*.

The purpose of the change is to enable these patients who experienced a relapse to be included in the local extension study CACZ885GFR01 with no time limitation after the end of study visit.

Canakinumab is still not commercially available in France in the SJIA (Systemic Juvenile Idiopathic Arthritis) indication at the date of the amendment 5. The inclusion in the local extension study is the only option to treat these patients and to resume canakinumab, when medically justified.

- Section 5. Treatment

For patients previously included in study CACZ885G2301E1 (SJIA), the option to interrupt canakinumab after a prolonged remission according to the investigators judgment has been added.

Every patient withdrawn from CACZ885GFR01 study due to a remission will be allowed to resume canakinumab in case of relapse and will be followed up again in the study.

- Section 5.1.1 . Investigational treatment

Novartis has been supplying the open-label investigational drug (canakinumab) under the form of a lyophilisate in vial. A marketing authorization has been granted in February 2017 by the European

Commission for canakinumab as a solution for injection.

If necessary (for logistic reasons), Novartis may supply one or the other pharmaceutical form for the trial. There will not be any change for the patient in the way the medication is administered (subcutaneously).

Amendment 4

The purpose of amendment 4 is to modify the paragraph 4.1 (Inclusion criteria), to take into account particular situations of some patients who have been included in international phase III study CACZ885G2306, to enable them to be included in the local extension study CACZ885GFR01. This amendment is aiming:

- ▶ to extend the period to allow inclusion of patients for the patients who have completed the international CACZ885G2306 study and who successfully withdrew canakinumab treatment per protocol but with a disease relapse in the following months. After amendment 4, patients who will relapse **within one year from the End of study visit** (instead of within one year from end of treatment) will be allowed to participate in CACZ885GFR01 study.
- ▶ to add a new inclusion criteria to take into account the specific situation of the patients of CACZ885G2306 study, not randomized (after randomization closure), and who, according to the international protocol, are supposed to remain at 4 mg/kg every 4 weeks until the end of the study. After a stable and prolonged remission in part II the investigators may propose to reduce the canakinumab dose in the interest of the patients as proposed in current practice (but not allowed in the current protocol). These patients (3 to 5 patients), will be withdrawn from CACZ885G2306 study and will be allowed to participate in CACZ885GFR01 study to continue canakinumab treatment.

Amendment 3

The purpose of amendment 3 is to open the recruitment of study CACZ885GFR01 to patients who will complete:

- ▶ the phase III international study CACZ885N2301 designed to assess efficacy and tolerability of canakinumab in patients suffering from 3 rare Hereditary Periodic Fevers [TRAPS (TNF receptor associated periodic syndrome), HIDS (hyperimmunoglobulinemia D syndrome) or crFMF (colchicine resistant Familial Mediterranean Fever)],
- ▶ or the phase III international study CACZ885G2306 designed to assess 2 different canakinumab taper regimens in patients suffering from SJIA (Systemic Juvenile Idiopathic Arthritis) with clinical remission (inactive disease for at least 24 continuous weeks) on canakinumab treatment.

The objective is to provide continuous treatment to these patients once CACZ885N2301 and CACZ885G2306 are completed and until this medication is commercially available in France for these new indications.

Taking into account the status of these ongoing studies at the date of May 2016, we may anticipate that a maximum of 8 patients included in CACZ885N2301 (within 4 French centers) may be included in CACZ885GFR01 from November 2016 and that a maximum of 21 patients included in CACZ885G2306 (within 3 French centers) from October 2016.

The last visit of study CACZ885N2301 will be the first visit of study CACZ885GFR01. Patients will continue on their last dosing regimen of the open-label long term treatment epochs (Epochs 4) considered to constitute the lowest clinically efficacious doses to maintain clinical efficacy in individual patients. Patients may receive an up-titration if they re-flare (maximum dose of 300 mg/ 4 mg/kg for patients weighing ≤ 40 kg) q4w.

The follow-up of patients with Hereditary Periodic Fever will be the same as the one for patients with SJIA.

The last visit of study CACZ885G2306 will also be the first visit of study CACZ885GFR01. Patients will continue on their dosing regimen considered to constitute the lowest clinically efficacious dose to maintain clinical efficacy in individual patients.

The study duration of CACZ885GFR01 study will be extended until canakinumab (Ilaris[®]) is commercially available for all indications.

Changes to the protocol are related to the following sections:

- Section 1.1. Background
- Section 1.2. Purpose
- Section 3.1. Study design
- Section 3.3. Rationale of dose/regimen, route of administration and duration of treatment
- Section 3.5. Risks and benefits
- Section 4. Population
- Section 5. Treatment
- Section 6. Visit schedule and assessments
- Section 9.4. Analysis of variables

Amendment 2

The purpose of this study CACZ885GFR01 is to provide continuous Ilaris[®] (canakinumab) treatment to patients in France who completed Study CACZ885G2301E1 (long term phase III study) until this medication is commercially available and reimbursed in France for the systemic Juvenile Idiopathic Arthritis indication. The current version of the protocol stipulates that the treatment period will be a maximum 12 months or could end sooner if Ilaris[®] was commercially available in France.

Because it is anticipated that the reimbursement of Ilaris[®] (canakinumab) may not be achieved at actual date of study completion, the study duration will be extended (one year extension).

Changes to the protocol are related to the following sections:

- Section 1.1. Background
- Section 1.2. Purpose
- Section 3.1. Study design
- Section 6. Visit schedule and assessments

Amendment 1

The purpose of amendment 1 is to make clear that Novartis will supply the open-label investigational drug (canakinumab) from commercial packages or clinical batches.

Furthermore, amendment 1 also addresses the request from the investigators to add the option to reduce the canakinumab dose in patients with adequate response by prolonging the canakinumab dose interval (i.e. every 6 or 8 weeks) according to clinical response and investigators judgment.

Changes to the protocol are related to the following sections:

- Section 5.1.1 Investigational treatment
- Section 5 Treatment
- Section 6. Visit schedule and assessments

Protocol synopsis

Protocol number	CACZ885GFR01
Title	A French open-label extension study of canakinumab in patients who participated in international phase III studies CACZ885G2301E1 or CACZ885G2306 in Systemic Juvenile Idiopathic Arthritis and CACZ885N2301 in Hereditary Periodic Fever (TRAPS, HIDS or crFMF).
Brief title	French study extension to study CACZ885G2301E1, CACZ885G2306 and CACZ885N2301.
Sponsor and Clinical Phase	Novartis Pharma SAS III
Investigation type	Biological
Study type	Interventional
Purpose and rationale	
The purpose of this study is to provide continuous canakinumab (Ilaris®) treatment to patients in France who completed study CACZ885G2301E1, CACZ885G2306 or CACZ885N2301.
 
The local extension study will be completed as soon as canakinumab is commercially available and reimbursed in France for these indications, or if applicable, when it will be confirmed that the last indication could not be reimbursed in France. However, as the commercialization of the different indications will be effective at different dates, patients will discontinue the study indication by indication.
 
This study will only be proposed to French centers involved into study CACZ885G2301E1, CACZ885G2306 and CACZ885N2301.

Objective(s)	The objective of this extension protocol is to collect safety data (serious and non-serious adverse events) and to provide continuous canakinumab to patients in France who completed study CACZ885G2301E1, CACZ885G2306 or CACZ885N2301 until a decision regarding reimbursement in France is effective for canakinumab (Ilaris®) in these indications.

Study design	
This is an open-label (single treatment arm) extension safety study for patients who completed the international studies:
 
• CACZ885G2301E1• or CACZ885N2301• or CACZ885G2306 
The last visit of study CACZ885G2301E1, CACZ885G2306 or CACZ885N2301 will be the first visit of this extension study.
 
Patients follow up:
 
For patients previously included in study CACZ885G2301E1 (SJIA indication)
 
These patients will continue the same dosing regimen used at the end of CACZ885G2301E1.
 
Visits will take place at canakinumab dose administrations, approximately every 4 weeks (or less frequently according to investigators judgment i.e. 6, 8 or 12 weeks). The safety of canakinumab will be evaluated (adverse events and serious adverse events collection). Patients will be followed up according to SmPC (see appendix 1) and local practice.
 
For patients previously included in study CACZ885N2301 (Periodic Fever syndromes)
 
These patients will continue the maintenance dose as determined at the end of the open-label period/ epoch 4 (i.e the lowest clinically efficacious dose to maintain clinical efficacy in individual patients with a good tolerability).
 
Visits will take place at scheduled administration dates, approximately every 4, 8 or 12 weeks. The safety of canakinumab will be evaluated (adverse events and serious adverse events). Patients will then be followed up according to SmPC approved by EMA (European Medicines Agency).
 
For patients previously included in study CACZ885G2306 (SJIA)
 
These patients will continue on their dosing regimen considered to constitute the lowest clinically efficacious dose to maintain clinical efficacy in individual patients.
 
Visits will take place at canakinumab dose administration, approximately every 4, 8 or 12 weeks. The safety of canakinumab will be evaluated (adverse events and serious adverse events collection). Patients will be followed up according to SmPC (see appendix 1) and investigators judgment.

Population	
Up to 40 patients may be included in the French extension study CACZ885GFR01 (in 3 centers).
 
• Twelve patients previously enrolled into study CACZ885G2301E1• Up to 28 potential additional patients according to amendment 3:
○ Up to 21 patients included in CACZ885G2306 study (in 3 French centers)○ Up to 7 patients included in CACZ885N2301 study (in 3 French centers).

Inclusion criteria	
Criteria applicable for patients with Systemic Juvenil Idiopathic Arthritis SJIA)
 
▶ Patients who have completed the international studies CACZ885G2301E1 or CACZ885G2306 without any significant safety issue according to Investigator's opinion.▶ Patients who have completed the international CACZ885G2306 study and who successfully withdrew canakinumab treatment per protocol but with a disease relapse after the end of study visit will be allowed to participate in CACZ885GFR01 study (whatever the time of relapse from the end of study visit), if the investigator states that there is an indication to resume canakinumab.▶ Patients who have participated in the international CACZ885G2306 study but could not be randomized and then have continued canakinumab in part I until the end of the study at a dose of 4 mg/kg every 4 weeks may be switched to CACZ885GFR01 study if the investigator thinks that, in the interest of the patient, there is an indication to taper off canakinumab dose after a prolonged remission. 
Criteria applicable for patients with Periodic Fever syndromes (TRAPS, HIDS, crFMF)
 
▶ Patients who have completed the international CACZ885N2301 study without any significant safety issue according to Investigator's opinion. 
Criteria applicable for all patients
 
▶ Parent's or legal guardian's written informed consent and child's assent, if appropriate, or patient's written informed consent for patients ≥ 18 years of age must be obtained before any study related activity or assessment is performed.
Exclusion criteria	
1. History of recurring infections, or underlying conditions which may predispose them to infections. Treatment with canakinumab should not be continued in patients with severe infections requiring medical intervention.2. Hypersensitivity to the active substance or to any of the excipients (see SmPC, section 6.1).3. Concomitant use of second line agents such as disease-modifying and/or immunosuppressive drugs will not be allowed with the exception of:
• Methotrexate, and folic/folinic acid supplementation (according to standard medical practice)• Non-steroidal anti-inflammatory drug (NSAID)• Systemic corticosteroid treatment.4. Concomitant use of another biologic agent or any investigational drug.5. Pregnant or nursing (lactating) female patients, where pregnancy is defined as the state of a female after conception and until the termination of gestation, confirmed by a positive hCG laboratory test or an urinary pregnancy test.6. Female patients who are of child-bearing potential defined as all females physiologically capable of becoming pregnant, unless they are using effective methods of contraception during dosing of study treatment.

Treatment	
All patients will be treated with canakinumab.
 
For patients previously included in study CACZ885G2301E1 (SJIA)
 
These patients will continue the same dose as their last dose administered in the study CACZ885G2301E1: canakinumab 4mg/kg (or 300mg max) or 2mg/kg (150mg/max) every 4 weeks (or less frequently according to investigators judgment i.e. 6, 8 or 12 weeks).
 
For patients previously included in study CACZ885G2301E1, the canakinumab dose interval may be prolonged (i.e. every 8 or 12 weeks) in patients with adequate response according to the clinical response and investigators judgment.
 
For patients previously included in study CACZ885N2301 (Periodic Fever syndromes)
 
These patients will continue on their last dosing regimen of the open-label long term treatment epochs (Epochs 4) considered to constitute the lowest clinically efficacious dose to maintain clinical efficacy in individual patients.
 
Patients will then continue one of the following regimen:
 
- Canakinumab 150 mg (or 2 mg/kg for patients weighing ≤40 kg) q4w- Canakinumab 150 mg (or 2 mg/kg for patients weighing ≤40 kg) q8w- Canakinumab 300 mg (or 4 mg/kg for patients weighing ≤40 kg) q4w- Canakinumab 300 mg (or 4 mg/kg for patients weighing ≤40 kg) q8w. 
In case of re-flare (according to investigators judgment), patients will be allowed to increase the dose as follows:
 
- If patients receive canakinumab 150 mg q8w, the dose of canakinumab will be increased to 150 mg q4w- If patients receive canakinumab 150 mg q4w, the dose of canakinumab will be increased to 300 mg q4w- If patients receive canakinumab 300 mg q8w, the dose of canakinumab will be increased to 300 mg q4w. 
For patients previously included in study CACZ885N2301, the canakinumab dose interval may be prolonged (i.e. every 8 or 12 weeks) in patients with adequate response according to the clinical response and investigators judgment.
 
For patients previously included in study CACZ885G2306 (SJIA):
 
These patients will continue the same dose as their last dose administered at the end of the tapering period study CACZ885G2306.
 
Then, patients will continue one of the following regimens:
 
- Canakinumab 4mg/kg q4wks- Canakinumab 2mg/kg q4wks- Canakinumab 1mg/kg q4wks- Canakinumab 4mg/kg q8wks- Canakinumab 4mg/kg q12wks. 
Patients may receive an up-titration if they re-flare (maximum dose of 300 mg (or 4 mg/kg s.c for patients ≤40 kg) q4w).
 
Patients who successfully withdrew canakinumab per protocol but with a disease relapse will be allowed to participate in CACZ885GFR01 study (whatever the time of relapse from the end of study visit) and will receive a starting dose of 4 mg/kg s.c (300 mg for patients ≥40 kg) every 4 weeks. This dose (or dose interval) may be adjusted according to the response and investigators judgment.
 
For patients previously included in study CACZ885G2306, the canakinumab dose interval may also be prolonged (i.e. every 8 or 12 weeks) in patients with adequate response according to the clinical response and investigators judgment.
 
For all indications, the maximum canakinumab dose is 4 mg/kg or 300 mg for patients ≥ 40 kg.

------------------	--

Investigational treatment	Novartis has been supplying the open-label investigational drug (canakinumab) under the form of a lyophilisate in vial. A marketing authorization has been granted in February 2017 by the European Commission for canakinumab as a solution for injection. If necessary (for logistic reasons), Novartis may supply one or the other pharmaceutical form for the trial. There will not be any change for the patient in the way the medication is administered (subcutaneously).
Efficacy assessments	There is no efficacy assessment in this study
Safety assessments	AEs and SAEs will be collected
Other assessments	None
Data analysis	
The data will be presented in a descriptive manner. Adverse events will be coded using the MedDRA dictionary that provides the primary system organ class and preferred term information.
 
Adverse events will be summarized for each indication by presenting the number and percentage of patients having any adverse event, having any adverse event in each primary system organ class and having each individual adverse event based on the preferred term. All other information collected (e.g. severity, relationship to study drug, or microorganism for infectious adverse events) will be tabulated and listed as appropriate.
 
Deaths, serious adverse events, and adverse events leading to discontinuation of study drug will be summarized by primary system organ class and preferred term and listed.
 
The exposure to study drug (number of injections) and duration of exposure (days) will be summarized and listed.

1 Introduction

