In case of use of oral contraception women should have been stable on the same pill for a minimum of 3 months before taking study treatment.

Reliable contraception should be maintained throughout the study and until 3 months after canakinumab discontinuation.

5 Treatment

Initial canakinumab dose:

For patients previously included in study CACZ885G2301E1 (SJIA)

Patients will continue the same dose as their last dose administered in the study CACZ885G2301E1: canakinumab 4mg/kg (or 300mg max) or 2mg/kg (150mg max) every 4 weeks.

Canakinumab dose reduction from 4 mg/kg to 2 mg/kg every 4 weeks in steroid-free patients with prolonged strong response was permitted in the ongoing extension study CACZ885G2301E1 at the request of the treating physician and with the agreement of Novartis.

Similarly, in this study, the canakinumab dose may be reduced from 4mg/kg (300 mg max) to 2mg/kg (150 mg max) every 4 weeks and then interrupted after a prolonged remission according to the investigators judgment.

For patients previously included in study CACZ885N2301 (Periodic Fever syndromes indications: TRAPS, HIDS or crFMF)

Patients will continue one of the following regimens as received at the end of the study:

- canakinumab 150 mg (or 2 mg/kg for patients weighing ≤ 40 kg) q4w
- canakinumab 150 mg (or 2 mg/kg for patients weighing ≤ 40 kg) q8w
- canakinumab 300 mg (or 4 mg/kg for patients weighing ≤ 40 kg) q4w
- canakinumab 300 mg (or 4 mg/kg for patients weighing ≤ 40 kg) q8w

In case of re-flare (according to investigators judgment), patients will be allowed to increase the dose as follow:

- If patients receive canakinumab 150 mg q8w, the dose of canakinumab will be increased to 150 mg q4w
- If patients receive canakinumab 150 mg q4w, the dose of canakinumab will be increased to 300 mg q4w
- If patients receive canakinumab 300 mg q8w, the dose of canakinumab will be increased to 300 mg q4w

For patients previously included in study CACZ885G2306 (SJIA):

The patients will continue the same dose as their last dose administered at the end of the tapering period study CACZ885G2306.

Then, patients will continue one of the following regimens:

- Canakinumab 4mg/kg q4wks
- Canakinumab 2mg/kg q4wks
- Canakinumab 1mg/kg q4wks
- Canakinumab 4mg/kg q8wks
- Canakinumab 4mg/kg q12wks

The patients who have withdrawn canakinumab per protocol may resume canakinumab after a relapse at a starting dose of 4 mg/kg (maximum 300 mg) every 4 weeks.

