Dose adjustments (for all patients):

Patients may receive an up-titration or may resume canakinumab if they re-flare (maximum dose of 300 mg (or 4 mg/kg s.c for patients ≤ 40 kg q4w).

The canakinumab dose interval (i.e. every 6, 8 or 12 weeks) may also be prolonged in patients with adequate response according to investigators judgment.

Every patient withdrawn from CACZ885GFR01 study due to a remission will be allowed to resume canakinumab in case of relapse and will be followed up again in the study.

Canakinumab will be administered at the study center.

End of treatment

For patients treated for SJIA:

Investigators will be informed as soon as this indication is commercially available in order to organize at the next planned visit the dropout of the patients. If no visit is planned within 2 months of notification reception, the investigators will have to contact the patient in order to organize patient's study termination. Investigators will have the possibility to perform a last canakinumab administration during the last visit of the protocol.

For patients treated for TRAPS, HIDS and crFMF:

Investigators will be informed as soon as this indication is commercially available in order to organize at the next planned visit the dropout of the patients. If no visit is planned within 2 months of notification reception, the investigators will have to contact the patient in order to organize patient's study termination. Investigators will have the possibility to perform a last canakinumab administration during the last visit of the protocol.

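### The synopsis and section 5 give different starting doses for CACZ885G2306 patients who relapse after stopping canakinumab; read literally, they differ from 40 kg to just under 75 kg

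*Protocol*

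**What the plan says.** The protocol states the restart dose for these patients twice.

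- **Synopsis, Treatment:** they "will receive a starting dose of 4 mg/kg s.c (300 mg for patients ≥40 kg) every 4 weeks". The next sentence adds: "This dose (or dose interval) may be adjusted according to the response and investigators judgment".
- **Section 5, Treatment, initial dose:** they "may resume canakinumab after a relapse at a starting dose of 4 mg/kg (maximum 300 mg) every 4 weeks". No weight threshold appears.

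Other dose statements bear on how the synopsis bracket should be read.

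- The last line of the same synopsis cell uses the same threshold in a maximum: "For all indications, the maximum canakinumab dose is 4 mg/kg or 300 mg for patients ≥ 40 kg".
- Section 5, dose adjustments for all patients: "Patients may receive an up-titration or may resume canakinumab if they re-flare", with a "maximum dose of 300 mg (or 4 mg/kg s.c for patients ≤ 40 kg q4w". The synopsis has a similar weight-banded maximum for up-titration of CACZ885G2306 patients, directly before the restart sentence.
- The Periodic Fever regimens in section 5 use 40 kg to switch from weight-based to flat dosing, for example "canakinumab 300 mg (or 4 mg/kg for patients weighing ≤ 40 kg) q4w".
- Section 5.1.1 limits any single dose to 300 mg.
- Section 5.5.5 leaves dose changes to the investigator's judgment.
- Section 3.3 refers SJIA patients to the SmPC in Appendix 1, whose text is not in the documents reviewed.

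**The concern.** These are two statements of a starting dose for the same patients, and they do not say the same thing. The synopsis bracket names a dose and a weight from which it applies, which reads as a flat 300 mg from 40 kg. Section 5 has a weight-based dose with a ceiling. Two sites that both follow the protocol could start the same relapsed patient on different doses.

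What is at stake is clarity about the first dose after relapse, not overdosing. Section 3.5 relies on adherence to the protocol's dosing guidance to limit risk, and that calls for a single rule. There is also a small reporting effect. Exposure is summarised by dose (protocol 9.3) and by mg/kg group (SAP 2.4.1), and a 300 mg start at 50 kg, which is 6 mg/kg, fits none of the named groups and would fall under other doses.

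**Working it through.** The protocol gives no figure of its own to reproduce here, so the check is to compute each rule by body weight *w* (kg).

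**Rules**

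- Synopsis, read literally: 300 mg if *w* ≥ 40, otherwise 4 × *w*.
- Section 5: the smaller of 4 × *w* and 300 mg.
- Section 5 maximum on up-titration or resumption: 300 mg if *w* > 40, otherwise 4 × *w*.

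The section 5 cap binds when 4 × *w* = 300, that is at *w* = 300 / 4 = 75 kg.

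| Weight (kg) | Synopsis (mg) | Section 5 (mg) | Difference (mg) | Ratio | Synopsis (mg/kg) |
|---|---|---|---|---|---|
| 39.9 | 159.6 | 159.6 | 0 | 1.00 | 4.00 |
| 40 | 300 | 160 | 140 | 1.88 | 7.50 |
| 45 | 300 | 180 | 120 | 1.67 | 6.67 |
| 50 | 300 | 200 | 100 | 1.50 | 6.00 |
| 60 | 300 | 240 | 60 | 1.25 | 5.00 |
| 70 | 300 | 280 | 20 | 1.07 | 4.29 |
| 75 | 300 | 300 | 0 | 1.00 | 4.00 |
| 80 | 300 | 300 | 0 | 1.00 | 3.75 |

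The literal rules therefore differ for 40 ≤ *w* < 75 and agree elsewhere. The gap is largest at 40 kg and shrinks by 4 mg for each further kilogram.

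**Do the stated maxima settle it?** No. At 50 kg both 200 mg and 300 mg are within the 300 mg single-dose limit and within the section 5 maximum for patients who resume. A ceiling that admits both doses cannot choose between them. The permission to adjust in the synopsis depends on response, so it applies after the first dose.

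**Alternative reading.** If the synopsis bracket is a cap on 4 mg/kg, the synopsis dose is also the smaller of 4 × *w* and 300 mg, and the difference is 0 at every weight. The 40 kg threshold then does nothing, because the cap cannot bind below 75 kg.

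**Boundary at exactly 40 kg.** The maximum is 4 × 40 = 160 mg under section 5, which puts 40 kg in the weight-based band, and 300 mg under the synopsis, which puts 40 kg in the flat band. This affects one weight only.

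**Number of patients.** The synopsis and section 4 allow up to 21 patients from CACZ885G2306. The documents give neither their weights nor the number who relapsed after withdrawal.

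**The case against.** The strongest reply is that the dose gap exists under only one of two readings. In the synopsis, the other 40 kg phrases that apply to CACZ885G2306 patients, namely the up-titration limit and the closing line for all indications, state maxima. The flat-dose convention comes from another indication. Redundant wording is common in a synopsis, so an idle threshold is not proof of a flat dose. The SmPC may also settle the question for the sites. Finally, dose variation at the investigator's discretion is part of the design, and the study is descriptive with no hypothesis test.

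Much of this stands. The cap reading cannot be excluded, the SmPC cannot be checked here, and the consequences are small. But the argument from neighbouring sentences cuts both ways. A weight-banded ceiling just before the restart sentence makes it natural to read that sentence as starting patients at the ceiling. The same cell also uses plain maximum wording for the CACZ885G2301E1 doses when a cap is meant. Two defensible readings of a starting dose are the defect, and discretion to adjust later does not supply the first dose.

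**Conclusion.** The inconsistency is real and in current text. Read literally, the starting doses differ from 40 kg to just under 75 kg, by up to 140 mg (1.88 times) at 40 kg and by 100 mg (1.50 times) at 50 kg. That size assumes the synopsis bracket is a flat dose; as a cap, the difference is zero and only the wording conflicts.

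It should be corrected because it bears on what a patient is given, but its practical weight is low. Neither dose exceeds the 300 mg single-dose limit, and above 40 kg both are within the section 5 maximum for resumption. The affected group is an unknown part of at most 21 patients, possibly none. The adverse-event tables and the safety set do not change.

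**What to change.** In a written amendment under section 11.1, state one starting-dose rule for these patients in identical words in the synopsis and section 5, after checking it against the SmPC in Appendix 1. Section 5's wording, 4 mg/kg up to 300 mg, fits the mg/kg SJIA regimens under the single-dose limit; the choice is the sponsor's. In the same amendment, use one non-overlapping boundary for the maximum dose (≤40 kg and >40 kg).

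Separately, and whichever rule is chosen, widen deviation S01 in SAP 5.5. It names only 2 and 4 mg/kg as protocol doses, although section 5 also permits "Canakinumab 1mg/kg q4wks" and flat 150 or 300 mg in Periodic Fever patients above 40 kg (at 50 kg, 150 / 50 = 3 and 300 / 50 = 6 mg/kg). S01 excludes nobody from the safety set, and the SAP already plans to update the list before database lock, so this is a wording edit.

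The cost is one amendment, which can be combined with the next planned one, with sponsor and ethics approval, health authority approval where required, and notice to the French sites. No extra patients or procedures are needed.
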